### **Exploratory Outcomes:**

1. Using a standardize nasal wash procedure, respiratory samples will be collected at enrollment, at end of study, and during acute respiratory illness requiring face-to-face provider interaction. Children with a tracheostomy will have both a nasal wash sample and a tracheal aspirate sample collected. The respiratory samples will be stabilized with a universal transport media, processed and stored at -80 C for future testing. Testing will be performed for cytokines/chemokines; other biomarkers of disease such as LDH, MPO, and caspase; viral and bacterial respiratory pathogens; and microbiome.
2. To determine if prophylactic use of azithromycin will reduce level of airway resistance as measured by an Airwave Oscillometry System in subjects above 2 years of age, at the time of respiratory illnesses, during the 3-6 months intervention.
3. To determine if prophylactic use of azithromycin will reduce the total number of unscheduled face-to-face physician visit for respiratory related illness in a clinic, urgent care, emergency room or hospital setting during the following 12 months after the intervention.

## Background

For the past 3 years, the High Risk Children's Clinic at UTP (HRCC) has been providing a medical home for medically complex children. We have demonstrated major benefits (e.g., 50% fewer serious illnesses & 55% fewer hospital days) and savings (~\$10K/child/year) from the comprehensive care provided in our enhanced medical home to high-risk chronically ill children--including patients with chronic lung disease (CLD). These benefits have not been previously shown for medical homes for patients of any kind or age. These benefits result primarily from 24/7 access by phone to dedicated and experienced caregivers directed by a pediatric pulmonologist. The clinic offers same day appointments and provides comprehensive coordination of care for this population. We now aim to further cut morbidity rates by developing specific outpatient interventions to augment comprehensive care for each major disorder that we treat.

A significant portion (44%) of our patients in the High Risk Children clinic are chronically ill children who have some form of CLD including patients with bronchopulmonary dysplasia (BPD). Chronic lung disease, as defined by the ATS statement from 2002, is "a heterogeneous group of respiratory diseases of infancy that usually evolves from an acute respiratory disorder experienced by a newborn infant." Specifically, infants with bronchopulmonary dysplasia, defined as the need for supplemental oxygen therapy in children past 28 days born under 32 weeks gestation. These infants often incur long-term pulmonary function abnormalities, including oxygen dependency after discharge, recurrent respiratory infections, and other reactive airway diseases. From our data, we have learned that many of the hospital admissions in our group of patients were related to respiratory infections (37%) during the winter season. Despite vaccination rates of nearly 100%, administration of Palivizumab to all of those eligible patients and access to our comprehensive care clinic, viral respiratory illnesses continue to cause considerable

morbidity and high healthcare costs. Innovative new prophylactic treatments are needed.

Macrolides have received considerable attention for their anti-inflammatory and immunomodulatory actions beyond the antibacterial effect. Such properties may ensure some efficacy against a wide spectrum of respiratory viral infections. Recent studies, including a study performed in our lab with elderly BALB/c mice infected with RSV, have shown that the high mortality rate of respiratory virus infections is a result of a neutrophilic overactive inflammatory response. A recently published study examined the inflammatory response in hospitalized infants with RSV and evaluated the predictive value of cytokines in nasopharyngeal aspirate in comparison to disease severity and found an increase in Th1 and Th2 cytokines. Respiratory viral infections are characterized by the appearance of cytokine storms which are an extreme production and secretion of numerous pro-inflammatory cytokines. Severity of infection is closely related to virus-induced cytokine dysregulation, which is responsible for the development of fatal clinical symptoms, such as massive pulmonary edema, acute bronchopneumonia, alveolar hemorrhage, and acute respiratory distress syndrome. Macrolides down-regulate the inflammatory cascade, attenuate excessive cytokine production in viral infections, and may reduce virus-related exacerbation. Clinical trials have demonstrated controversial results in the effects of macrolides in respiratory viral infections. To date, studies have only evaluated macrolide use as a treatment, not as a prophylactic therapy. Long-term therapy with the macrolide antibiotic erythromycin was shown to alter the clinical course of diffuse pan bronchiolitis in the late 1980s. Since that time, macrolides have been found to have a large number of anti-inflammatory properties in addition to being antimicrobials. These observations provided the rationale for many studies performed over the last decade to assess the usefulness of macrolides in other inflammatory airways diseases, such as cystic fibrosis, asthma, COPD, and bronchiolitis obliterans syndrome. One RCT looked at the daily use of macrolides for up to six weeks to prevent bronchopulmonary dysplasia in premature infants in a NICU setting and found the neonates to have better outcomes without an increase in adverse effects. However, chronic use of macrolides

has not been studied to prevent respiratory infection complications in patients with CLD of infancy. We will test the hypothesis that prophylactic macrolides are effective in reducing the severity of respiratory viral illness and that this is associated with the prevention of the full activation of an inflammatory cascade.

## **Study Design and Methods**

### *Overview:*

This pilot randomized control trial (RCT) will enroll 92 children from 6 months to <6 years of age that have chronic lung disease (CLD) such as bronchopulmonary dysplasia during two seasons of respiratory illnesses defined as 1st October to 31st March of each year (2015-2016 Season and 2016-2017 Season). If the minimum number of patients (n=92) in Season 1 is achieved, we will then perform an interim analysis of the data. These children will all be patients who receive their primary medical care from either the High Risk Children Clinic or the similar High Risk Infant Clinic that cares for premature infants from discharge until age 2. Clinic records will be screened to determine eligibility. Patients that have parental consent will be given a baseline EKG, a nasal aspirate, an oscillometer reading (over 2 years of age only), and a three to six month supply of either the medication or the placebo at an initial study visit. Both medications will be taken once a day for three days a week: Monday, Wednesday and Friday. The azithromycin medication will be dosed at 5 mg/kg/day. Adjustments in dosage amount will be made with any new weights obtained during the trial period. Any child that is eligible to receive Palivizumab will be given this every 28-30 days in clinic as per usual care. Patients will be followed on a monthly basis and closely monitored for adverse reactions; this will occur by phone, in clinic during their regularly scheduled appointments, and/or during any necessary illness visits. Any children with adverse reactions will discontinue the medication, but will continue to be followed clinically. At any clinic visit in which a child presents with respiratory infections, including pneumonia,

upper respiratory illness, bronchiolitis, etc., he/she will have an additional nasal aspirate and/or tracheal aspirate if applicable and an oscillometer reading (only for children >2 years) performed. At the completion of the 3-6 months treatment phase, each child will have a final nasal aspirate and/or tracheal aspirate if applicable, and an oscillometer reading performed. Data will continue to be collected for the following 2 months (April 1st to May 31st), to monitor for respiratory illnesses and possible side effects.

*Study Population:*

High risk children between the chronological age of 6 months and 6 years who attend either the High Risk Children's Clinic or the High Risk Infant Clinic at UTP will be screened by the research nurse, and additional help will be provided by the clinic providers. The high risk infant clinic follows premature infants born before 32 weeks gestation for their first 2 years of life; the high risk pediatric clinic follows medically complex children who have had at least 3 ED visits, 2 hospitalizations, and/or 1 PICU visit within the last year for a chronic health condition.

*Inclusion/Exclusion Criteria:*

Children who belong to either the High Risk Infant Clinic or the High Risk Children's Clinic and that have been diagnosed with a chronic lung disease as defined by ATS by a medical provider will be included. Chronic lung disease (CLD) is the final common pathway of a heterogeneous group of pulmonary disorders that start in the neonatal period. Often the inciting factor is bronchopulmonary dysplasia (BPD), a chronic condition that can develop after premature birth and respiratory distress syndrome due to surfactant deficiency. Myriad other conditions can also cause airway and parenchymal inflammation that leads to chronic airflow obstruction, increased work of breathing, and airway hyper reactivity. Usually the inciting factors are not only the underlying disorders, but also the effects of the supportive treatment, including mechanical ventilation, barotrauma, and oxygen toxicity. These aggressive interventions for serious neonatal and infant lung diseases are often responsible for much of the chronic pulmonary abnormalities that follow. Exclusion criteria include

children with cystic fibrosis or bronchiectasis, because the prophylactic use of macrolides has already demonstrated value and become usual care for these patients. Children with cardiac arrhythmias will be excluded, due to the potential increase in cardiovascular death that has been shown in the adult population. Patients with cyanotic heart disease would be excluded. Children with colitis will also be excluded due to the potential effects to the gastrointestinal flora. In addition, any child with a known macrolide allergy or child who is taking any medication that has a known interaction with macrolides, and any child with kidney or liver failure will also be excluded. Patients with short-bowel syndrome would also be excluded due to malabsorption of medication.

Once patients are screened for eligibility, families will be approached, either over the phone or at a regularly scheduled office visit. Informed written consent will be obtained in the clinic from the parent or legal guardian of each eligible child by any of the co-investigators or the research nurse at the time of enrollment. Either the research nurse or another clinical member of the HRCC team will then collect a nasal aspirate sample at the first study visit (description in Laboratory section). The nasal aspirate will be stored and studied after the conclusion of the treatment phase for its levels of myleoperoxidase, cytokines, respiratory virology, and micro biome. In addition, all patients 2 and older will have a spirometry reading performed using a TremoFlo airway oscillometry system (iOS) manufactured by Thorasys. With the iOS, the child breathes normally into the machine and lung function is measured by a gentle multi-frequency airway against the patient's respiratory airflow. A baseline EKG will be obtained on all patients.

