## **Data Analysis Plan**

Patients will be randomized to one of two different branches by the REDCap data base randomization program. This will be a double-blind placebo controlled study. Standard frequentist and Bayesian analyses will be performed using an intent-to-treat approach. Total hospital days, total ER visits (counting one day for each ER visit), and unscheduled clinic visits (counting one day for each visit) for respiratory symptoms will be analyzed and related to treatment (Azithromycin vs Placebo), with logistic regression models and the treatment group as a covariate and random intercept to account for within patient correlation (due to multiple ED visits). To assess the probability of benefit, we will use Bayesian hierarchical models with interaction terms between treatment groups (Azithromycin vs Placebo) and predefined potential moderators. The groups will be stratified by palivizumab use and by tracheostomy on chronic mechanical ventilation. The conservative Bayesian approach of Dixon and Simon allows us to shrink the subgroup estimates to the overall mean treatment effect. For all Bayesian analyses, prior distributions for main effects will be neutral  $\sim N(0,1000)$ , and Uniform (0,1000) for SD parameters. Neutral and skeptical priors will be used for interaction terms. Point estimates of treatment effect and 95% credible intervals will be reported along with probability of treatment benefit.

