## **Sample size and power**

Based on data from our HRCC, we expect the control group to have 1.6 encounters per child-year (SD=1.66). Assuming a two-sided alpha = 0.05, a sample size of 90 (45/group) will have 80% power to detect a difference of 1 in the encounter rate between placebo and azithromycin groups (i.e., 1.6 vs 0.6 in encounter rate or 38% reduction). Power will be more limited for secondary outcomes but Bayesian analyses will provide an estimate of the probability of benefit in these outcomes.

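### The primary model adjusts for neither clinic of origin nor prior-year use, although the two clinics enrol on different grounds and the planning rate describes only one of them

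*Combined protocol and SAP*

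**What the plan says.** **Who is enrolled.** Under Study Population, the two sources are described differently. For the infant clinic: "The high risk infant clinic follows premature infants born before 32 weeks gestation for their first 2 years of life". For the HRCC: "medically complex children who have had at least 3 ED visits, 2 hospitalizations, and/or 1 PICU visit within the last year", for a chronic condition. Every participant also needs a provider diagnosis of chronic lung disease, and the Overview calls the two clinics similar.

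**What the sample size rests on.** Sample size and power gives a control rate of 1.6 encounters per child-year with SD 1.66, introduced by "Based on data from our HRCC". It continues: "Assuming a two-sided alpha = 0.05, a sample size of 90 (45/group) will have 80% power" and "to detect a difference of 1 in the encounter rate between placebo and azithromycin groups". No rate, SD or expected enrolment share is given for the infant clinic.

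**How the outcome is analysed.** The Data Analysis Plan names regression models with treatment and a patient random intercept. It then says "The groups will be stratified by palivizumab use and by tracheostomy on chronic mechanical ventilation". That sentence sits within the Bayesian subgroup text, and the sentences on REDCap randomisation name no strata, so it is unclear whether even these two factors restrict allocation. The Bayesian models add interactions with moderators that are called predefined but are not listed. Neither clinic of origin nor prior-year use is named as a stratum or a model term.

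**The concern.** One source selects children on recent ED, hospital or PICU use, which overlaps with the primary outcome of unscheduled respiratory encounters. The other has no utilisation rule and covers only the first two years of life. Clinic and prior-year use are therefore likely to predict encounter counts.

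Two things follow. First, a model with treatment alone leaves that predictable variation in the residual and does not correct for a chance difference between arms in clinic mix or past use. In a trial of about 46 children per arm this costs precision. Second, a rate and SD from HRCC records are not shown to describe the mixed population that will be randomised, so the meaning of the powered difference is uncertain.

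**Working it through.** **Inputs from the plan.** Control rate 1.6 per child-year, SD 1.66, difference 1.0, two-sided alpha 0.05, 45 per group (Sample size and power); 92 children (Overview), allocated half and half (Study Procedures), so 46 per arm; expected reduction 20% (Study Outcomes).

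**Assumptions, because the plan gives no figures.** Half the children come from each clinic; the infant-clinic rate is 0.8, varied from 0.4 to 1.2; the correlation r between prior-year count and outcome is 0.3 to 0.5; 1.66 is the SD of the enrolled mix.

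**1. The plan's own figure.** n per group = 2 × (1.96 + 0.842)² × 1.66² / 1² = 43.3, so 44. At 45 per group the power is 81.5% (normal) or 80.7% (t-test). The stated 90 is reproduced.

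**2. Chance imbalance in clinic mix.** SD of the between-arm difference in clinic share = √(2 × 0.5 × 0.5 / 46) = 0.104. The shift in the treatment difference is the imbalance times the gap D between the clinic rates.

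| Infant-clinic rate | D | 1-SD shift | 1.96-SD shift | Mixed control rate | 20% of mixed rate |
|---|---|---|---|---|---|
| 1.2 | 0.4 | 0.04 | 0.08 | 1.4 | 0.28 |
| 0.8 | 0.8 | 0.08 | 0.16 | 1.2 | 0.24 |
| 0.4 | 1.2 | 0.13 | 0.25 | 1.0 | 0.20 |

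In the central case the 1.96-SD shift is 0.163/0.32 = 51% of a 20% effect at the stated rate of 1.6, 0.163/0.24 = 68% of a 20% effect at the mixed rate, and 16% of the powered difference.

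**3. What adjusting for clinic gains.** Share of outcome variance due to clinic = 0.25 × D² / 1.66² = 0.16 / 2.756 = 5.8%. The standard error falls by 1 − √(1 − 0.058) = 2.9%. If 1.66 were instead the SD within each clinic, the total variance would be 2.756 + 0.16 = 2.916 and the share 5.5%, which changes little.

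**4. What adjusting for prior-year count gains.** The standard error falls by 1 − √(1 − r²): 4.6% at r = 0.3 and 13.4% at r = 0.5. With 45 per group:

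| Model | Power for 1.0 | Power for 0.32 |
|---|---|---|
| Unadjusted | 82% | 15% |
| r = 0.3 | 85% | 16% |
| r = 0.5 | 91% | 18% |

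Steps 3 and 4 use linear-model formulas. The plan names logistic regression, so they indicate scale only.

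**5. The planning rate.** At 1.6, a difference of 1 is 1/1.6 = 62.5%, not the 38% stated (38% of 1.6 is 0.61). At mixed rates of 1.4, 1.2 and 1.0 it would be 71%, 83% and 100%.

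**The case against.** **Chance imbalance is not bias.** Randomisation makes it zero on average, and the standard error already covers it if 1.66 describes the enrolled mix. This stands, with the reservation that 1.66 is an HRCC figure.

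**A reader might infer that clinic imbalance could rival the expected effect.** The documents do not support that as a general statement. Against 0.32, none of the tabulated shifts gets there: the 1.96-SD values are 26%, 51% and 77% of it. With 45 per arm and a 50:50 mix, a 1.96-SD imbalance reaches 0.32 only if D is at least 1.55, which means an infant-clinic rate near zero. Against 20% of the mixed rate, an infant-clinic rate of 0.4 gives 0.245/0.20 = 123%, but there one assumed figure both raises the shift and lowers the target, and the event is still in the tail. For prior-year use, the 1.96-SD limit reaches 0.32 only if r is about 0.47 or more.

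**The clinics may not differ much.** Their entry rules are different, not opposite; a child could meet both. HRCC entry counts use for any chronic condition, not only respiratory illness, and the Background reports about half as many serious illnesses under that clinic's care, so use at clinic entry need not describe later use. Nothing establishes that the infant-clinic rate is lower. All this stands, and it is why every size above is conditional.

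**The plan may already cover part of this.** The unlisted moderators could include clinic, and palivizumab use may partly track it. That is possible, but a plan that does not name the variables does not prespecify them.

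**Conclusion.** The concern holds as a modest loss of efficiency plus an unverified planning rate. The differing entry rules, the single-clinic source of 1.6 and the treatment-only model are plain in the text. The size is not: it depends on the clinic mix, the infant-clinic rate and the correlation with prior use, none of which the documents give. Under the central assumptions a typical clinic imbalance moves the contrast by 0.08 per child-year, and clinic adjustment alone brings little. Prior-year use is the more valuable covariate, and only if it correlates reasonably with the outcome. The change is worth making because it is cheap and improves the analysis. It does not rescue power: a 20% effect at 1.6 needs 423 per group unadjusted, and power stays below 20% at 45 per group even with r = 0.5.

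**What to change.** - **Data Analysis Plan:** prespecify clinic of origin and prior-year respiratory encounter rate as enrolment covariates in the primary model. For children under 1 year, express the rate per month observed. Fix both before any unblinded look, including the interim analysis that the Overview allows for. List the moderators for the Bayesian models.
- **Sample size and power:** either state that 1.6 (SD 1.66) describes HRCC children only, or recompute both from eligible children under 6 with chronic lung disease in the two clinics' records. Then restate the relative reduction that a difference of 1 represents.
- **Optional:** clinic as a further randomisation stratum. With the two factors already named, this makes eight cells for 92 children, about 11.5 each, so the covariate route is the safer minimum.

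**Cost:** two model terms, a reworded planning paragraph and a short record look-up. Clinic is known for every child. Prior-year counts must be extracted, and they will be less stable in infants because the look-back is short.

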#### *Study Procedures:*

Patients will be randomized by the REDCap statistical program in a double blind manner. Parents will then be provided with a medication or placebo for the duration of the study. Patients would be recruited for this study on a rolling basis from October 1st to December 31st, and all patients completing the intervention part of the protocol on 31st March at the end of the season. Half of the patients will receive azithromycin at a

dose of 5 mg/kg to be given once a day on Monday, Wednesday, and Friday. The other half, the control group, will be provided with a placebo medication of similar taste, color, texture, and consistency, also to be taken once a day on Monday, Wednesday, and Friday. Both the study medication and the placebo will be dispensed from Corner Compounding Pharmacy, mixed with a fish-oil base to ensure a shelf life of more than six months, and flavored with citrus to improve palatability. Parents will be contacted biweekly, either in clinic or by phone, to monitor for any adverse reactions, including rash, nausea, vomiting, diarrhea, or abdominal cramping. If a significant adverse reaction occurs, the medication will be discontinued. If an allergic reaction (such as rash or shortness of breath) is noted, the blind will be broken by Research Coordinator [name], who is not involved with the project. This un-blinding will be done to note if it is an allergy to the medication.

After the initial appointment, at any face to face encounter (unscheduled sick visit or hospital admission Monday through Friday) in which the patient presents with respiratory symptoms, the patient will be evaluated by the research nurse or one of the co-investigators. Specifically, if a patient presents with the following symptoms: cough, wheeze, tachypnea, rhinorrhea, increased respiratory secretions, hypoxemia, and/or an increased oxygen requirement, an additional nasal aspirate sample/and tracheal aspirate if applicable, and an oscillometry reading (for patients over 2 years of age) will be performed. These samples will also be stored in the office of [name]. At the conclusion of the 3-6 months treatment phase, a final nasal aspirate/and tracheal aspirate if applicable sample. Oscillometer reading will also be performed for those above 2 years of age while the patients are in clinic for an office visit at the end of the study visit and during each sick clinic visit for respiratory illness. There will be no expected/additional study visits and no compensation will be provided for parents or patients.

*Risks:*

Potential risks include an allergic reaction or adverse reaction to the medication or placebo. Examples of potential side effects include nausea, vomiting, diarrhea, and skin

reactions. In addition, there may be an increased risk of diaper rash and/or oral thrush with the increased use of antibiotics. Another adverse outcome of azithromycin has been an increase in pyloric stenosis with both prenatal and infant exposure for the first 4 months of life, and benefit in this age group must outweigh this potential risk. However, our population for this project will begin at 6 months of age. Each of these risks and any other unexpected outcomes will be monitored at any visits to the clinic, or with biweekly phone calls if no visits have been scheduled in the previous two weeks. The primary benefit we hope to see is a reduction in the number of respiratory illness related office visits. With the anti-inflammatory properties of the macrolide, we predict an overall reduction in the severity of respiratory illnesses during the study period. Additionally, we will monitor data for a 2 month period following last azithromycin administration. This reduction may lead to a decrease in the number of unscheduled office visits, emergency room visits, and hospital admissions. With less face to face provider encounters, there will be less opportunity for potential exposure to other viruses, as well as less time away from home or work for the patients' parents and, potentially, decreased health care related costs.

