### **Secondary Aim:**

1. To determine if the administration of azithromycin will have similar number of adverse side effects, or adverse events leading to unscheduled clinic, urgent care, emergency room or hospital visit as compared to placebo during the 3-6 month study period and the following 2 months.
2. To determine if the use of azithromycin will reduce healthcare cost associated with respiratory illness during the 3-6 month study period and 2 month follow-up period.

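### Cardiac risk motivates an exclusion, but cardiac events are not named in on-study safety monitoring and get no by-arm line, so the planned safety conclusion would not show them

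*Combined protocol and SAP*

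**What the plan says.** **Before dosing.** Under Inclusion/Exclusion Criteria: "Children with cardiac arrhythmias will be excluded, due to the potential increase in cardiovascular death that has been shown in the adult population". The same section adds "Patients with cyanotic heart disease would be excluded" and "A baseline EKG will be obtained on all patients". No reason is stated for the EKG.

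**During treatment.** Study Procedures has staff contact parents every two weeks "to monitor for any adverse reactions, including rash, nausea, vomiting, diarrhea, or abdominal cramping". The Risks section mentions allergic reactions and gives examples: nausea, vomiting, diarrhea and skin reactions. It then says "there may be an increased risk of diaper rash and/or oral thrush with the increased use of antibiotics" and discusses pyloric stenosis. It closes the list with "Each of these risks and any other unexpected outcomes will be monitored at any visits to the clinic", or by phone if there has been no recent visit. None of these places names a cardiac event, and no later EKG is planned.

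**Analysis.** Item 1 of the Secondary Aim compares the arms on a "similar number of adverse side effects, or adverse events leading to unscheduled clinic, urgent care, emergency room or hospital visit". Study Outcomes item 5 expects no significant difference in side effects. The Data Analysis Plan specifies models only for hospital days, ER visits and unscheduled clinic visits for respiratory symptoms. It has no safety table or model. The section on interpretation of findings nevertheless lists, among the things the trial will determine, whether azithromycin has a safety profile similar to placebo.

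**The concern.** A harm that led to an exclusion would normally reappear in what is asked about during treatment and in what is reported at the end. Here it does neither. Many of these children are too young to describe a symptom, and a parent may not connect an episode with the drug unless asked. An event that nobody asked about cannot be recovered at analysis.

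If a cardiac event is recorded, the only planned by-arm comparison is a total, in which it counts the same as one episode of diarrhea. What is at stake is the safety conclusion, which could be read as covering a harm that the trial neither asked about by name nor displayed. The primary efficacy comparison is not affected.

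**Working it through.** **1. Exclusions set against on-study monitoring**

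| Safety concern at entry | Counterpart after dosing starts |
|---|---|
| Macrolide allergy | Rash asked about at contacts; unblinding rule for allergic reactions (Study Procedures) |
| Colitis, because of gut flora | Diarrhea and abdominal cramping asked about (Study Procedures) |
| Arrhythmia, because of cardiovascular death in adults | None named in Study Procedures, Risks or Data Analysis Plan |

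The Risks section also discusses pyloric stenosis, which it then sets aside because enrolment starts at 6 months. It does not mention the cardiac risk cited for the exclusion.

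**2. Arm size.** No figure in the plan concerns cardiac events, so only the arm size carries over. Sample size and power gives SD 1.66, difference 1, two-sided alpha 0.05 and 80% power: n = 2 × (1.960 + 0.842)² × 1.66² / 1² = 43.3, so 44 per arm. The stated 45 per arm gives 81.5% power, so the plan's figure reproduces. The Overview plans 92 children and Study Procedures assigns half to azithromycin, which gives 46 per arm.

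**3. What zero events would exclude.** The exact upper limit with 0 events in n children is 1 − a^(1/n).
- One-sided 95%, n = 46: 1 − 0.05^(1/46) = 6.3%.
- Upper end of a two-sided 95% interval, n = 46: 1 − 0.025^(1/46) = 7.7%.
- With n = 45 these become 6.4% and 7.9%.

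These limits assume that every event is found. Prompting makes that assumption more credible but cannot bring the figure down.

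**4. Chance of seeing any event in the azithromycin arm**, 1 − (1 − p)^46. The documents give no cardiac risk, so p is assumed over a range.

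| Assumed true risk p | Chance of at least one event |
|---|---|
| 0.1% | 4.5% |
| 1% | 37% |
| 2% | 61% |
| 5% | 91% |

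**5. Whether a total would show it.** Assume 20% or 40% of children in each arm have some other adverse event, and azithromycin adds an independent cardiac risk c. The azithromycin proportion is then 1 − (1 − base)(1 − c). Power is for a two-proportion comparison with 46 per arm and two-sided 5% alpha, counting only results in the direction of harm (2.5% by chance alone).

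| Base | c | Azithromycin proportion | Power |
|---|---|---|---|
| 20% | 2% | 21.6% | 3.8% |
| 20% | 5% | 24.0% | 6.7% |
| 40% | 2% | 41.2% | 3.3% |
| 40% | 5% | 43.0% | 4.8% |

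Power is about 3% to 7%, little above chance. Base rates and c are assumptions.

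**6. Whether a separate line could be tested.** With 46 per arm, Fisher's exact test gives p = 0.056 for 5 versus 0 and p = 0.026 for 6 versus 0. A cardiac line is therefore descriptive, not a test.

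**The case against.** The strongest reply is that capture is open. The contact list gives examples of any adverse reaction, the Risks section also covers unexpected outcomes, and the Secondary Aim counts adverse events leading to any unscheduled visit, whatever the organ system. A serious cardiac event would usually lead to such a visit. Excluding susceptible children and then monitoring generally is also a coherent approach, and nothing in the plan forbids a breakdown by type. Finally, the missing safety analysis applies to every kind of adverse event, not only cardiac ones.

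Most of this stands, and it rules out several stronger readings that a reader might infer:

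- *Cardiac events will go unreported.* The text supports only that they can, because nothing prompts for them.
- *The safety conclusion rests on skin and gut complaints alone.* It does not, because the open wording and the visit-based count admit other events.
- *Every child is screened by EKG because of cardiovascular death.* That reason is attached to the arrhythmia exclusion. A link to the EKG is inference.
- *The plan regards cardiac harm as expected in eligible children.* It speaks of a potential increase, shown in adults.
- *The 6.3% limit measures the damage done by the omission.* It follows from 46 children in the arm.

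The reply does not reach two things. Open wording records what someone volunteers, and it is no substitute for asking about a risk that the protocol itself cites. And permission to break the total down is not a plan to do so.

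**Conclusion.** The point holds as a gap in ascertainment and reporting that is cheap to close. The arrhythmia exclusion cites a cardiac risk, no section names that risk after dosing starts, and the only by-arm safety comparison is a total. A recognised event could be recorded, but it would not be visible in that total: power is about 3% to 7% for an added risk of 2% to 5%, under assumed background rates of 20% to 40%. A non-significant total therefore cannot support a statement that safety is similar where a rare cardiac harm is concerned.

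Even with complete ascertainment, 0 of 46 leaves a risk of up to 6.3% (one-sided) or 7.7% (two-sided) unexcluded. This rests on all 92 children being enrolled and split equally. The share of cardiac events that would go unmentioned without a prompt is unknown, because the documents give no basis for estimating it.

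**What to change.** 1. **Study Procedures and Risks.** Reconcile these with the Inclusion/Exclusion Criteria by making cardiac events a named category at the parent contacts and encounter reviews already planned. The clinical terms are for the investigators to set.
2. **Data Analysis Plan.** Report adverse events by type and by arm. Give cardiac events a separate descriptive line with an exact upper confidence limit (stating whether one- or two-sided), alongside the baseline EKG result of each affected child. This also fills the general gap in safety reporting.
3. **Study Outcomes item 5 and the interpretation section.** Do not infer similarity from a non-significant pooled difference. State what the trial can exclude, for example 6.3% (one-sided 95%) or 7.7% (two-sided 95%) if 0 of 46.

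No additional EKG, visit or stopping rule is proposed, and the sample size is unchanged. The cost is one more category at existing contacts and an adverse-event table by type. A few events unrelated to the drug will be recorded in both arms, and the safety claim becomes narrower.
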